## 1.5 Compliance Statement

This study will be conducted in full accordance all applicable Children's Hospital of Philadelphia Research Policies and Procedures and all applicable Federal and state laws and regulations including 45 CFR 46, 21 CFR Parts 50, 54, 56, and 312.. All episodes of noncompliance will be documented.

The investigators will perform the study in accordance with this protocol, will obtain consent and assent, and will report unanticipated problems involving risks to subjects or others in accordance with The Children's Hospital of Philadelphia IRB Policies and Procedures and all federal requirements. Collection, recording, and reporting of data will be accurate and will ensure the privacy, health, and welfare of research subjects during and after the study.

## 2 STUDY OBJECTIVES

2.1 The purpose of the study is to determine if a proton-pump inhibitor will improve the efficacy of pancreatic enzyme replacement therapy as evidenced by changes in

fat absorption and to characterize the mechanism by which this improvement occurs. Primary Objective (or Aim)

2.2 The primary objective of this study is to determine if a proton-pump inhibitor improves fat malabsorption in subjects with CF and EPI who are on pancreatic enzyme replacement therapy. The primary outcome measure of fat absorption will be the gold standard coefficient of fat absorption (CFA). Secondary Objectives (or Aim)

The secondary objectives are to:

- Determine if changes in duodenal pH on and off acid suppression occur using the SmartPill®, and if such changes correlate with changes in fat absorption.
- Characterize changes in triglyceride absorption on and off acid suppression using the malabsorption blood test.
- Explore associations among changes in nutrition status (weight, height, BMI), GI symptoms, and quality of life in subjects treated with omeprazole vs. placebo in combination with PERT.

#### 3 INVESTIGATIONAL PLAN

## 3.1 General Schema of Study Design

This is a randomized placebo-controlled double-blinded trial with a crossover design to determine the efficacy of omeprazole as an adjunct to PERT to improve dietary fat absorption in 24 adolescent (12+ years) and adult subjects with CF and EPI. Refer to Table 3 for a description of the flow of the study design.

## 3.1.1 Screening Phase

Subjects will be recruited from the CF Centers at the Children's Hospital of Philadelphia (CHOP), hospitals affiliated with University of Pennsylvania, and other regional CF Centers. Potential subjects will be screened using the protocol inclusion and exclusion criteria. Twenty-four subjects with CF and EPI, 12 years of age and older, will be recruited, with a goal of 50% of subjects between the ages of 12 and 18. Subjects who are receiving PPI or H2 medication will be eligible, but must be willing to discontinue this medication use as needed to comply with the protocol. Subject or parent/guardian informed consent and, if applicable, child assent, will be obtained prior to any study-related procedures being performed, including discontinuation of current therapy. A stool sample will be collected to confirm eligibility based on exocrine pancreatic insufficiency as measured indirectly by fecal elastase if a fecal elastase has not already been documented in the medical record. Height and weight will also be obtained as a baseline. Subjects will be asked to follow a moderate to high fat diet and also to continue their clinically-established standard PERT dose for the duration of the study.

## 3.1.2 Study Treatment Phase (start of the study intervention)

There will be a 14-day period prior to the start of the study intervention during which time all subjects will maintain a standard diet/PERT dose. Subjects who were taking PPIs or H2 medication at the time of the screening/consent visit, will discontinue these medications for the duration of the study. This 14-day period prior to the start of the intervention will also serve as a washout period from these medications for these subjects. After this 14-day period, treatment with omeprazole or placebo will commence. After completing 28 days of treatment with omeprazole or placebo, subjects will have a second study visit, during which the first set of assessments will be completed. All study visits will occur at outpatient research offices of the Center for Human Phenomic Science (CHPS) at The Children's Hospital of Philadelphia (CHOP), a pediatric health care center. Eligible subjects will be enrolled into the study and come to CHOP for the study visits. Refer to Table 1 for list of assessments and the study timeline for the pace of recruitment.

## 3.1.3 Second Treatment Phase

After completing the second study visit, there will be a 14-day washout period during which subjects will discontinue their study medication but continue their standard diet/PERT use. Subjects will then cross over to the other treatment arm and undergo an additional 28 days of treatment with omeprazole or placebo. At the end of this treatment period, they will have a third study visit that will include the outcome measure assessments.

#### 3.2 Allocation to Treatment Groups and Blinding

Subjects (n=24) will be randomized at the consent visit. Subjects will be randomized to receive either omeprazole (n=12) or placebo (n=12) for 28 days. The randomization scheme will be generated and executed by the University of Pennsylvania Investigational Drug Service (IDS) pharmacy. All other research personnel will be blinded to the randomization throughout the study. The randomization code will be maintained by the University of Pennsylvania IDS Pharmacy. In a medical emergency, the primary investigator [name] be unblinded to the participant's study medication at any time to provide the needed information for clinical care.

#### 3.3 Study Duration, Enrollment and Number of Sites

## 3.3.1 Duration of Study Participation

The study duration per subject will be up to 100 days, with one day for screening and consent, up to 48 days each for Phases 1 and 2 for the washout and treatment periods, as well as the assessment visits, totaling approximately 100 days. No follow-up is required upon completion of the study procedures.

## 3.3.2 Total Number of Study Sites/Total Number of Subjects Projected

The study will be conducted at one investigative site in the United States, the Children's Hospital of Philadelphia. Recruitment will occur across regional centers as described above.

Recruitment will stop when 24 subjects with CF and EPI have been enrolled. It is expected that 24 subjects will be enrolled to produce 22 evaluable subjects in each group to account for attrition.

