Study Rationale	Fat malabsorption contributes to poor nutritional status in people with cystic fibrosis (CF) and exocrine pancreatic insufficiency (EPI). Gastric acid-reducing agents such as proton pump inhibitors (PPI) are prescribed as adjunct medications to pancreatic enzyme replacement therapy (PERT) to improve dietary fat absorption through a mechanism that reduces gastrointestinal acidity. There is insufficient evidence that this approach improves duodenal pH, nutritional outcomes, or fecal fat loss as measured by the coefficient of fat absorption (CFA) in patients with CF. We propose a randomized placebo-controlled double-blinded trial with a crossover design to determine the efficacy of the commonly-prescribed PPI, omeprazole, as an adjunct to PERT to improve dietary fat absorption in 24 adolescent (≥12 years) and adult subjects with CF and EPI. After a 14-day washout period, subjects (12 in each group) will be randomized to receive 28-day treatment with either omeprazole or placebo while maintaining a moderate-to-high fat diet and standard PERT regimen. Upon completion of the first arm of the study, subjects will again undergo a 14-day washout period and cross over to the other treatment arm for an additional 28 days. Dietary fat absorption will be determined using the stool CFA as the primary outcome. The other outcomes include change in duodenal pH (SmartPill® wireless capsule) and improved fat absorption as indicated by the malabsorption blood test (MBT). By changing the gastroduodenal pH, omeprazole may improve fat absorption compared to placebo.						
Study Objective(s)	
 
Primary Hypothesis:
 
Omeprazole, a commonly-prescribed PPI, in combination with pancreatic enzyme replacement therapy (PERT) will significantly improve dietary fat absorption compared to placebo in subjects with CF and EPI as indicated by CFA.
 
						
	MBT Quality Improvement Project						
	The primary objective of this Quality Improvement project is to enroll two adults to have an MBT. The results will be used to determine which laboratory the research group will use for future processing and analysis of the MBT samples.						
	Cocondow, Hymotheses						

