There is limited evidence from randomized placebo-controlled trials that agents such as omeprazole that reduce gastric acidity, when used as adjunctive therapy with PERT are associated with improvement in fat absorption. Heijerman and colleagues, in a randomized controlled trial with a crossover design, found a reduction of 4.8% in fecal fat excretion in 11 subjects receiving 14-days of omeprazole compared to when they received 14-days of placebo (18.1 % vs. 22.9%, respectively). In another study using a similar crossover design, the same authors found a reduction in fecal fat excretion of 8.9%, from 19.6% after 14-day placebo treatment to 10.7% after 14-day omeprazole treatment in 9 subjects on high dose pancreatic enzyme therapy. Proesmans et al, using a randomized crossover design in a study of 15 children with CF and confirmed steatorrhea, found a reduction 7.5 g of fecal fat (from 13.0 to 5.5 g) and an increase in CFA of 7% (from 87 to 94%) after one month of omeprazole use. In other clinical trials of H2 acid blockers as adjunctive therapy to PERT, CFA% improved from 77.1 to 83.6% in a study of 10 children with CF receiving PERT only, compared to PERT plus cimetidine over 14-day periods, and from 74.4% to 87.3% in 10 CF children receiving PERT only and PERT plus famotidine over 6-month periods. In our proposed randomized controlled trial with a crossover design, 22 subjects (11 randomized to 28-day treatment and 11 to placebo at Visit 1, then crossing over to the alternate treatment for 28-days) will have 80% power to detect an increase of 3% with omeprazole treatment compared to no change (0%) when on placebo with a common SD of 5% using a paired t-test with  $\alpha$  =0.05.

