We have not based the samples size upon the secondary exploratory hypotheses, however, the effect sizes that can be detected with our sample size of 22 subjects can be estimated. For the MBT method, the sample size is based upon our previous experience in CF with detecting differences in Cmax and AUC for HA and the HA/PA ratio4, and in detecting the percent change in HA absorption (from pharmacokinetic modeling) compared to healthy subjects5. For our proposed study, with the crossover design, 22 subjects (11 in each randomization group) will have 80% power to detect a difference in means of 0.60 (the difference in Cmax (in AUC) HA/PA ratio, with a mean of 1.62 (1.30) for omeprazole treatment, compared to 1.02 (0.70)) for placebo: this is a 37% increase in Cmax and 46% increase in AUC with omeprazole treatment compared to placebo, assuming that the common SD is 0.68 using a paired t-test with  $\alpha$  =0.05. For the CFQ-R domain scores, a sample size of 22 subjects with provide 80% to see an increase of 9 points (i.e. from 80 to 89) with omeprazole treatment compared to placebo with a common SD of 15 points using a paired t-test with  $\alpha$ =0.05. For the SmartPill®, Gelfond has demonstrated significantly lower duodenal pH in subjects with CF compared to healthy controls. The outcome of interest is the time that it takes for the pH to reach 5.5, the minimum level required to dissolve the enteric coating from PERT so that they are effective for nutrient absorption. In a study of 10 subjects with CF compared to 10 healthy controls using the SmartPill® methodology, the time required to reach a pH of 5.5 in CF was 17.7±6.8 compared to  $6.3\pm6.4$  In controls (p=0.004). We expect a subsample of 12 subjects to be 18+ years of age and use the SmartPill® for duodenal pH assessment. A sample of 10 subjects is required for 80% power to see a reduction in time to pH of 5.5 in the GI tract from 17 to 11 minutes

with omeprazole treatment compared to placebo, with a common SD of 7 minutes, using a paired t-test with  $\alpha$ =0.05.

Using this randomized crossover design, a total sample of 22 subjects, 11 in each randomization group will be needed. Therefore, enrolling 24 subjects (12 in each group) will result in 22 subjects completing the study if we experience 10% attrition.

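### Section 3.3.2 gives 22 evaluable subjects in each group where section 6.4 needs 22 in total, and 10% attrition from 24 leaves 21.6, not 22

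*Combined protocol and SAP*

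**What the plan says.** Section 3.3.2 sets the enrolment limit and the expected evaluable sample in consecutive sentences: "Recruitment will stop when 24 subjects with CF and EPI have been enrolled", and then "It is expected that 24 subjects will be enrolled to produce 22 evaluable subjects in each group to account for attrition".

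Section 6.4 states the requirement differently: "a total sample of 22 subjects, 11 in each randomization group will be needed". It then links this to enrolment: "enrolling 24 subjects (12 in each group) will result in 22 subjects completing the study if we experience 10% attrition". The power sentence for the primary endpoint says that 22 subjects, 11 starting on each treatment, "will have 80% power to detect an increase of 3% with omeprazole treatment compared to no change (0%) when on placebo". The assumptions given there are an SD of 5%, a paired t-test and alpha 0.05.

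The sizes of the randomized groups appear elsewhere too. Section 3.2: "Subjects will be randomized to receive either omeprazole (n=12) or placebo (n=12) for 28 days". The Study Rationale in the Protocol Synopsis: "subjects (12 in each group) will be randomized to receive 28-day treatment". Section 6.3.2 again gives 12 and 12 for the two randomization groups.

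**The concern.** The number of evaluable subjects is a basic design figure and should read the same wherever it appears. Here one section gives 22 per group and another gives 22 overall. On the protocol's own group sizes, the first cannot be met.

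The attrition step is a second, smaller mismatch. The plan names a loss rate and a completer count that do not quite agree, and the stated 80% power is attached to that count. At stake is whether the evaluable size and the power are stated correctly, so that the final report can be checked against them.

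**Working it through.** **Inputs.** Enrolment 24 (3.3.2); 12 per randomized group (3.2, Synopsis, 6.3.2, 6.4); required size 22 in total, 11 per randomization group (6.4); attrition 10% (6.4); difference in CFA 3 points, SD 5%, paired t-test, alpha 0.05 (6.4). Two inputs are assumptions. The documents do not say whether 5% is the SD of the within-subject difference or of a single measurement; I take the former. They do not say whether the test is one- or two-sided; I take two-sided.

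**1. Reproducing the 22.** Normal approximation for a paired comparison:

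n = [SD × (z₀.₉₇₅ + z₀.₈₀) / difference]² = [5 × (1.960 + 0.842) / 3]² = 21.8, rounded up to 22.

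So 22 is a total number of subjects, as 6.4 says.

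**2. Can 3.3.2 be met?** A randomized group has 12 subjects, and 22 exceeds 12. With 22 completers split evenly, each randomization group holds 22 / 2 = 11, as in 6.4. The 3.3.2 sentence is arithmetically possible only if group means treatment condition: 22 completers each measured on both treatments give 22 on omeprazole and 22 on placebo.

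**3. Attrition.**
- 24 × (1 − 0.10) = 21.6 completers.
- Two losses: 2 / 24 = 8.3%, leaving 22.
- Three losses: 3 / 24 = 12.5%, leaving 21.
- Working backwards, 22 / 0.90 = 24.4, which rounds up to 25 rather than 24.

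**4. Power at those counts.** Two-sided paired t-test, noncentral t with n − 1 degrees of freedom and noncentrality (3 / 5) × √n:

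| Completers | Noncentrality | Power |
|---|---|---|
| 24 | 2.94 | 80.4% |
| 22 | 2.81 | 76.5% |
| 21 | 2.75 | 74.4% |

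The gap at 22 is 80 − 76.5 = 3.5 points. It arises because the normal approximation yields 22 where the t-test itself needs 24. Moving from 22 to 21 completers costs a further 76.5 − 74.4 = 2.1 points.

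**5. Sensitivity to the assumptions.** One-sided, power is 85.9% at 22 and 84.4% at 21. If 5% is the SD of a single measurement, the SD of the difference is 5 × √[2(1 − ρ)], where ρ is the correlation between a subject's two measurements. Two-sided power at 22 is then 47.6% for ρ = 0, 59.2% for ρ = 0.25, 76.5% for ρ = 0.5 and 96.7% for ρ = 0.75.

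**The case against.** The best defence is that in a crossover every completer contributes to both treatments, so 22 completers do supply 22 evaluable on omeprazole and 22 on placebo. The heading of section 3.2 speaks of treatment groups, and section 5.2.1 frames the CFA comparison by treatment. This reading is possible, so the sentence should not be called flatly wrong on every interpretation. But section 3.2 itself puts 12 in each group, the Synopsis and 6.3.2 do the same, and 6.4 uses 12 enrolled and 11 completing. A per-treatment meaning would be unique to 3.3.2, and the sentence would still need rewording.

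It is also fair that 6.4 states the right figure more than once, that no calculation or test takes its size from 3.3.2, and that 21.6 rounds to 22. The power shortfall at 22 is separate from the group wording; it bears on the fix only because 6.4 attaches 80% to the completer count.

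Three stronger readings may tempt a reader, and the documents support none of them:
- That the trial needs 2 × 22 = 44 evaluable subjects and is under-enrolled. The sample size is for a paired test on 22 in total, and 3.3.2 itself caps enrolment at 24.
- That the unpaired comparisons between randomization groups are credited with twice their subjects. The plan claims no power for them, and 6.3.2 prints their sizes as 12 and 12.
- That the plan will often miss its target at 10% attrition. This treats a rounded planning rate as an exact, independent chance of loss for each subject, and rewording 3.3.2 would not alter it.

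**Conclusion.** The point holds as a minor correction of stated figures. Under the protocol's own use of the word when it gives sizes, 22 evaluable per group cannot come from groups of 12 and conflicts with the 22 in total of section 6.4. The attrition statement is off by 22 − 21.6 = 0.4 of a subject.

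With the SD of 5% taken as that of the within-subject difference and a two-sided test, the stated 80% power is about 76.5% at 22 completers and 74.4% at 21. Those two assumptions matter more than the attrition rounding, and the documents settle neither. Nothing here undermines the crossover design, the enrolment of 24 or the paired primary analysis.

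**What to change.** - **Section 3.3.2:** replace the per-group figure with *22 evaluable subjects in total (11 in each randomization group), each assessed on both treatments*.
- **Section 6.4:** choose one of two statements. Either give the allowance as no more than 2 of 24 lost (8%), or keep 10%, state about 21 completers and quote the power at that number.
- **Section 6.4, with either choice:** say which SD the 5% is and whether the test is two-sided, and give the matching power. Under the assumptions used here, that is about 76.5% at 22 or 74.4% at 21.

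The cost is wording in two sections and a slightly less favourable power figure. No extra enrolment, visit or procedure is involved.

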## 3.4 Study Population

#### 3.4.1 Inclusion Criteria

- 1) Males or females older than 12 years of age.
  - n=12 between 12 and 18 years of age
  - n=12 ≥18 years of age
- 2) Subjects must have the diagnoses of cystic fibrosis and exocrine pancreatic insufficiency (receiving PERT), with a pancreatic elastase <200 ug/g stool.
- 3) In usual state of good health no hospitalizations in the preceding two weeks.
- 4) Family and subject commitment to the approximately four month study protocol.

# 3.4.2 Parental/guardian permission (informed consent) and if appropriate, child assent. Exclusion Criteria

- 1)  $FEV_1 < 40\%$  of predicted.
- 2) Pregnant or lactating females.
- 3) Other illness affecting growth, fat absorption, or nutritional status.
- 4) Unwillingness to continue their clinically-established PERT dose for the duration of the study.
- 5) Use of other medication that affects dietary fat absorption.
- 6) Allergy to soy products
- 7) Allergy to safflower products (microlipids)
- 8) Parents/guardians or subjects who, in the opinion of the Investigator, may be non-compliant with study schedules or procedures.

In subjects ≥18 years of age, celiac disease or allergy to gluten will be an exclusion, as the SmartPill® study requires ingestion of a specialized meal that contains gluten. Subjects that do not meet all of the enrollment criteria may not be enrolled.

Any

violations of these criteria must be reported in accordance with IRB Policies and Procedures.

## 4 STUDY PROCEDURES

## 4.1 Consent Visit (Visit 1)

- Review of health history including prior and concomitant medications
- Review demographics
- Informed Consent
- Review of diet pattern
- Subjects asked to maintain a moderate to high fat diet throughout the study
- Subjects asked to maintain their clinically established PERT dose throughout the study
- Subjects asked to wean PPI or H2-receptor antagonist medication, if taking
- Simple anthropometrics
- Stool collection if needed
- Sexual maturity self-assessment (age <18y, n=12)

- GI symptom questionnaire
- Urine pregnancy test (female subjects)
- Distribute arm 1 study medication

Protocol	Day 1	Da	ys 2-15			Day	/s 16-43					
Visit 1: Consent and Randomization	- Clarify diet & PERT - Questionnaires - Elastase (if needed)			l-day washout p RA medication, i Istain on standar h fat diet onfirm standardi	f applicable rd moderate	to	- Randomized treatment to either omeprazole (PPI) or placebo for 28 days					
	Day 44	Day 45		Day 46	Day 47	Day	48	Day 49	Day 50	Days 51-		
Visit 2: After 28-day treatment with PPI or placebo	- Fast from 8pm - No dairy - Remain on standard PERT	- MBT - 7am-4p - Serum la - Anthros  If ≥18 yea - SmartPil - Fast fror 12am	bs a rs: ll	- Resume moderate- high fat diet If ≥18 years: - SmartPill at 8am - 6hr fast	- Diet record (day 1)	- Die reco (day - 72 Stoo (day	ord v 2) -hr ol	- Diet record (day 3) - 72-hr Stool (day 2)	-72-hr Stool (day 3)	- 14-day washout period from treatment placebo		

	Days 65-92	2 – Randomized	crossover treatn	nent (PPI to p	lacebo, or pla	acebo to PPI)	for 28 days	
	Day 93	Day 94	Day 95	Day 96	Day 97	Day 98	Day 99	Day 100
Visit 3:  After 28-day crossover treatment with placebo or PPI	- Fast from 8pm - No dairy - Remain on standard PEM	-MBT - 7am-4pm -Serum labs - Anthros  If ≥18 years: - SmartPill - Fast from 12am	- Resume moderate- high fat diet If ≥18 years: - SmartPill at 8am - 6hr fast	- Diet record (day 1)	-Diet record (day 2) - 72-hr Stool (day 1)	-Diet record (day 3) - 72-hr Stool (day 2)	-72-hr Stool (day 3)	- Return to usual care and medication regimen - Return to usual diet

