#### **MBT Quality Improvement Project**

The Principal Investigator (PI) ([name]) is ultimately responsible for monitoring the data integrity as well as the patient safety for this methods research development project. She will oversee all communication and scheduling prior to the MBT, participate in the consent process, and oversee all data analysis and collection.

Since the PI will be participating in this project and since other employees who report directly to the PI will be participating, we acknowledge that there is the risk of coercion. We want to make it clear that all participants were on this study prior to this amendment and are knowledgeable of the procedures and risks associated with the MBT.

Table 1: Schedule of Study Procedures Study Phase	Visit 1	Visit 2	Visit 3
July Filase	(Screening and Consent)	(Assessment 1)	(Assessment 2)
Assessment		,	,
Demographics	х		
Prior/Concomitant Medications	Х		
Randomization	Х		
Dispense Study Drug	Х	Χ	
Fecal elastase (if necessary)	X		
Urine pregnancy test	X		
Outcome Measures	-		
Coefficient of fat absorption		Χ	X
pH via SmartPill® (≥18y, n=12)		X	X
Malabsorption blood test		X	X
Serum vitamins A and E, essential fatty acids		Χ	X
Serum magnesium		Χ	X
Nutritional status			
Height, weight, BMI	X	X	X
Circumferences / skinfolds		Χ	X
Sexual maturity self-assessment (<18 y, n=12)	X		
Diet			
Diet pattern history	X		
Three-day weighed food record		X	X
Questionnaires			T
Health history	X	Χ	X
CF Quality of Life (CFQ-R)		X	X
Patient Reported Outcomes (PROMIS)		Χ	X
Demographics	X		
GI Symptom Questionnaire (PROMIS)	X	X	X
Adherence to Treatment, Enzymes		Х	X

Adverse Events	x	X
1 10 1 0 1 0 1 0 1 0 1 0 1		1

Table 2: Study Timeline

Table 2: Timeline					Yea	r 1 (	2018	3-19)									Yea	r 2 (	2019	9-20	)				
	Feb	Mar	Apr	Мау	Jun	Jul	Aug	Sept	Oct	Nov	Dec	Jan	Feb	Mar	Apr	Мау	Jun	Jul	Aug	Sept	Oct	Nov	Dec	Jan	Total
Start-up	Х	Х	Х	Χ	Χ																				
Visit 1: Consent				1	1	1	1	2	2	2	2	2	2	2	2	2	2								24
Visit 2: Assessment 1					1	1	1	1	2	2	2	2	2	2	2	2	2	2							24
Visit 3: Assessment 2							1	1	1	1	2	2	2	2	2	2	2	2	2	2					24
Visit Total				1	2	2	3	4	5	5	6	6	6	6	6	6	6	4	2	2					72
Sample and Data Analysis									X	Χ	Χ	Χ	Х	Χ	Χ	Χ	Χ	Χ	Χ	Х	Χ	Χ	Χ	Χ	
Closeout																							Χ	Х	

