## Day 2 - Visit to CHOP CHPS/NGL

- Insert blood-drawing intravenous catheter
- Baseline blood draw for MBT / study labs drawn (Vitamins A/E, Magnesium, essential fatty acids)
- Administer MBT study meal (breakfast)
- MBT hourly blood sample for 9 hours
- After hour 6, low-fat study lunch
- Anthropometry (height, weight, skinfolds, circumferences)
- Questionnaires: Health History and medications, Quality of life questionnaire (CF-QOL), PROMIS, GI symptom questionnaire, Adherence, Adverse Events

- Instructions will be given for collection and shipping for: stool collection (72-hour fecal fat analysis), 3-day weighed food records, and adverse events diary
- Provide arm 2 study medication
- SmartPill® cohort will fast overnight starting at 12:00am

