## 5.1.2.1 Pregnancy Testing

A urine pregnancy test will be performed for female subjects  $\geq$  9 years of age who are physically capable of becoming pregnant.

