Demographics and Health Questionnaire: The questionnaire will be administered via interview by the research staff, and will consist of two sections. The Health History section has general questions about the subject's health history including documentation of medical history, recent hospital admissions and illnesses, medication, history of pancreatic enzyme supplementation, and nutrient supplement use. The Health History section will be administered at all study visits. A Demographics section describes racial/ethnic status and insurance status of the research subject. In addition to subjects' contact information (name, address, phone numbers); contact information from two additional contacts will be collected to maintain contact with the subject in the event that the subject cannot be contacted at their primary residence. The demographic and contact information will be administered at Visit 1 only.

Quality of Life Questionnaires: In order to assess the health-related quality of life (QOL), validated questionnaires will be administered to all subjects at both Visits 2 and 3. The Cystic Fibrosis Questionnaire, Revised (CFQ-R, University of Miami) will be completed by the subjects. There is a questionnaire for subjects age 12-13, as well as a separate questionnaire for subjects greater than 14 years of age that is also validated in adults.

Patient Reported Outcomes (PROMIS): We will assess patient reported outcomes at both Visits 2 and 3 using the NIH-developed pediatric PROMIS short forms assessing pain, fatigue, depressive symptoms, physical function (mobility), and peer relationships. Adult subjects will use the corresponding adult forms. All subjects will use specific PROMIS short forms for GI symptoms including belly pain, diarrhea, gas and bloating, constipation, gastroesophageal reflux, and nausea and vomiting. These are valid and reliable scales broadly applicable across populations, GI symptoms, GI diseases and demographics.

Adherence: Adherence to both PERT and PPI will be assessed at study Visits 2 and 3, as well as by phone calls. This time will also be used to trouble-shoot any barriers to adherence, and also to collect information on adverse events experienced during the course of the study.

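### Pregnancy is an exclusion, but it is tested only at Visit 1 and not again before arm 2 study drug is provided at Visit 2

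*Combined protocol and SAP*

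**What the plan says.** Section 3.4.2 excludes "Pregnant or lactating females", and the synopsis carries the same exclusion. Neither says at what time it is to be verified.

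Testing appears in three places:

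- Section 4.1, the Visit 1 list: "Urine pregnancy test (female subjects".
- Table 1, the schedule of procedures: the row "Urine pregnancy test" has one mark, under Visit 1, and none under Visit 2 or Visit 3.
- Section 5.1.2.1: "A urine pregnancy test will be performed for female subjects" aged 9 or over who could become pregnant. It gives no visit and no repeat.

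Drug is handed out twice. At Visit 1, section 4.1 has "Distribute arm 1 study medication", in the same list as the test. At Visit 2 Day 2, section 4.2.1 has "Provide arm 2 study medication", with no test in the list. Section 7.1.1 makes each supply 33 days. Section 4.3 permits no unscheduled visits.

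**The concern.** Pregnancy status can change during a study of about 100 days. For arm 1, the plan tests at the visit where drug is dispensed. For arm 2, it dispenses on a result obtained at the start of the study. Either treatment sequence is affected, because arm 2 is omeprazole for some subjects and placebo for the others, and the staff handing it out are blinded.

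What is at stake is whether the protocol can show that its own exclusion held when the second supply was given. Visit 2 is the only scheduled visit between arm 1 dispensing and the second dosing period, so if the test is not repeated there, no scheduled visit remains at which to repeat it before dosing.

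**Working it through.** **Calendar.** The inputs are the day-by-day schedule in section 4.1 and the visit-day lists in sections 4.2.1 and 4.2.2. First, the protocol's own duration:

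Visit 1 (1) + washout (14) + treatment (28) + Visit 2 (7) + washout (14) + treatment (28) + Visit 3 (7) + return to usual care (1) = 100 days.

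This agrees with the approximately 100 days in section 3.3.1, so the day numbers can be used as they stand. Visit 2 occupies Days 44-50, and its Day 2 is study Day 45.

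**Age of the only test.** Age of result = event day − Day 1.

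| Event | Study day | Age of the Day 1 test |
|---|---|---|
| Arm 1 drug dispensed | 1 | 0 days (same visit) |
| First period-1 dose | 16 | 16 − 1 = 15 days |
| Arm 2 drug provided | 45 | 45 − 1 = 44 days |
| First period-2 dose | 65 | 65 − 1 = 64 days |
| Last period-2 dose | 92 | 92 − 1 = 91 days |

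**With the test repeated at Visit 2 Day 2.** Age at arm 2 dispensing = 45 − 45 = 0 days. Age at first period-2 dose = 65 − 45 = 20 days. The period-2 gap falls from 64 to 20 days, a reduction of 44, and becomes close to the 15 days that the plan already accepts for period 1.

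**Passages side by side.** The exclusion has no time attached, section 5.1.2.1 has no time attached, and Table 1 and section 4.1 agree on a single test at Visit 1. Nothing elsewhere supplies a repeat. The Visit 3 list also carries the line about providing arm 2 medication, but Table 1 and section 7.1.1 place dispensing at Visits 1 and 2 only, so nothing here rests on that line.

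**The case against.** The strongest reply is that section 3.4 sets enrollment criteria. A test at enrollment verifies an enrollment exclusion, and nothing says that the criteria must hold to Day 100. On that reading no two passages contradict each other, and this part of the reply stands. It does not settle the matter, because the protocol never says that the exclusion lapses after entry, and a second supply of study drug is a new exposure.

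Second, other safeguards exist. Adverse events are collected at Visits 2 and 3, by phone and by diary. The investigator reviews them, and section 4.5 allows withdrawal for safety. These could bring to light a pregnancy that a subject knows of and reports. None is a test, withdrawal is discretionary, and section 4.5 does not mention pregnancy.

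Third, section 9.4.2 names no pregnancy-related risk of omeprazole, and no section explains the exclusion. That is correct, so this point makes no claim about harm.

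Fourth, a repeat on Day 45 still leaves 20 days before dosing and does not change the 15 days before period 1. Both are true. The repeat shortens the period-2 gap but does not close it.

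A reader might go further and infer that general health, too, is checked only at consent. The criterion in section 3.4.1, "In usual state of good health no hospitalizations in the preceding two weeks", is indeed stated once, without a reference date. But section 5.1.3 says "The Health History section will be administered at all study visits", and that section of the questionnaire covers recent admissions and illnesses. It is taken on Days 45 and 94, three days before each stool collection begins (48 − 45 = 3; 97 − 94 = 3). The stronger reading is therefore not supported.

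**Conclusion.** The point holds for pregnancy. The one scheduled test is 44 days old when arm 2 drug is provided and 64 days old at the first period-2 dose, and no repeat is scheduled. This assumes that visits fall on the protocol's nominal days. The documents give neither a pregnancy rate nor the number of female subjects among the 24, so the size can be stated in days but not in expected cases.

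For health status, at most the plan does not say how a coefficient of fat absorption (CFA) value is handled when illness or an admission is recorded near the collection. That is a minor clarification. A reader might want to put a number on the resulting error in CFA, but the documents give no illness rate and no illness effect. In a blinded randomized crossover, illness unrelated to treatment would add noise rather than bias. Nor do the documents support dropping affected pairs as a remedy. Illness arises after randomization, and section 9.4.2 lists diarrhea and upper respiratory infection among events reported with omeprazole, so such exclusions could themselves introduce bias.

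**What to change.** Reconcile the schedule with the exclusion:

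- In Table 1, mark the urine pregnancy test under Visit 2 as well as Visit 1.
- In section 4.2.1, Day 2, list the test before the line on arm 2 medication, for the subjects defined in section 5.1.2.1.
- In section 5.1.2.1, state both time points.

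How a positive result is handled is for the investigator and the IRB to decide and document; this review proposes no rule.

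The cost is one urine dipstick per eligible female at a visit already scheduled, with no added visit. The remaining limitation is the 20 days between the Day 45 test and the Day 65 dose.

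Optionally, add one sentence to section 6.3.2 saying how recorded illness or admissions bear on the CFA value, so that this is settled before the data are seen.
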